### 3.4 Inclusion and Exclusion Criteria

#### Inclusion Criteria

1. Adult patient with aged  $\geq 18$  years old
2. Patients with pleural infection (complex parapneumonic effusion or empyema) with poor pleural fluid drainage of  $\leq 150$  ml after 24H of insertion of chest drain
3. Clinical features consistent with pleural infection ; fulfilling  $\geq 2$  of the following characteristics :
  - i) Clinical evidence of infection such as fever and or elevated C-reactive protein (CRP) or total white blood count (TWBC)
  - ii) Complex pleural effusion proven by thoracic ultrasound is defined as presence of fibrin strands or septations within pleural cavity
  - iii) Pleural fluid that fulfil at least one of the characteristic :
    - frank pus,
    - exudative type of pleural effusion (according to light's criteria)
    - gram stain or culture positive
    - lactate dehydrogenase (LDH)  $> 900$ U/L
    - Acidic with  $\text{ph} < 7.2$
    - glucose level  $< 3.3$  mmol/L

#### Exclusion criteria

1. Refusal to participate
2. Known allergy to t-PA or DNase
3. Acute stroke
4. Significant bleeding diathesis/ active gastrointestinal bleed
5. Major surgery in the previous 5 days
6. Previous pneumonectomy on the infected side
7. Bronchopleural fistula
8. Pregnancy

9. Coagulopathy (INR > 2, APTT > 100)
10. Platelet count < 50000 cells

### 3.5 Problem Statement

Retained complicated pleural effusion is associated with a risk of empyema and sepsis. IPFT is commonly used as the bridging therapy to surgery. The efficacy of saline irrigation is not known. However, the probable problem in this study is when failed saline irrigation, the patient will be given IPFT as part of the intention to treat.

### 3.6 Recruitment/Data Collection

Subjects with pleural infection (complex parapneumonic effusion or empyema) with poor outflow  $\leq 150$ cc pleural fluid from chest drain over 24 hours of insertion with standard medical therapy who are eligible for this study will be offered to participate into this study. Patient will be informed that this is an 'off label' drugs and a written informed consent will be obtained.

All patients will undergo chest tube/drain insertion. The decision to insert chest drain, the size of chest drain and when to initiate intrapleural t-PA/DNase is determined by the chest physician.

Ultrasound of thorax and chest radiograph will be performed within 24 hours before randomization. Ultrasound of thorax is performed by chest physician with curve probe (ultrasound Mindray, model Z5) for confirmation of complex pleural effusions and chest tube's position. Complex pleural effusion on ultrasound is defined as fibrin strands or septa within the pleural effusion along with presence of loculations in pleural cavity. A baseline chest radiograph will be performed within 24 hours prior to intrapleural fibrinolysis or pleural irrigation to ensure the chest tube position.

Demographic data was collected prior to randomization, which consist of age, gender, ethnicity, BMI, comorbidities. Subjects will be randomized with a block of 4 (using sealed envelope) with random permutations of 2 groups : pleural irrigation group and intrapleural t-PA and DNase.

All patients that prescribed intrapleural t-PA/DNase during the study period will receive a standard dose of medications as below (Appendix 1).

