## CHAPTER 3: METHODOLOGY

### Description of Methodology

#### 3.1 Study Design

Prospective open-label study on patients with pleural infection who were given either pleural irrigation or intrapleural t-PA and DNase from **June 2023 – June 2025** in Universiti Kebangsaan Malaysia (UKM) Medical Center

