#### 3.3 Sample size and Power of Study

By using power and sample size programme calculator :

Prior data indicate that the failure rate among controls is 0.15. If the true failure rate for experimental subjects is 0.32, we will need to study 39 experimental subjects and 39 control subjects to be able to reject the null hypothesis that the failure rates for experimental and control subjects are equal with

probability (power) 0.8. The Type I error probability associated with this test of this null hypothesis is 0.5. We will use a continuity-corrected chi-squared statistic or Fisher's exact test to evaluate this null hypothesis.

N = 39+/-4 (IPFT with alteplase and DNase) and 39+/-4 (pleural irrigation with normal saline)

Study used as a reference :

Pleural irrigation trial (PIT): a randomised controlled trial of pleural irrigation with normal saline versus standard care in patients with pleural infection Clare E. Hooper, Anthony J. Edey, Anthony Wallis, Amelia O. Clive, Anna Morley, Paul White, Andrew R.L. Medford, John E. Harvey, Mike Darby, Natalie Zahan-Evans and Nick A. Maskell,

Reference for sample size taken from the primary outcome of this research in which patients receiving saline irrigation had a significantly greater reduction in pleural collection volume on computed tomography compared to those receiving standard care (median (interquartile range) 32.3% (19.6–43.7%) reduction versus 15.3% (–5.5–28%) reduction) (  $p < 0.04$ ).

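### A fixed, published block of 4 in an open-label, single-centre trial could let a recruiter who tracks the sequence know about 25 of 78 allocations in advance

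*Combined protocol and SAP*

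**What the plan says.** Section 3.6 (Recruitment/Data Collection) gives the whole account of allocation: "Subjects will be randomized with a block of 4 (using sealed envelope) with random permutations of 2 groups". One block size is named and it is printed in the protocol. The only concealment measure is "using sealed envelope". Nothing is said about opacity, numbering, who prepares the list, who holds or opens the envelopes, or whether the block size is withheld from those who recruit.

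Section 3.1 describes a "Prospective open-label study on patients with pleural infection" conducted "in Universiti Kebangsaan Malaysia (UKM) Medical Center". Section 3.3 plans equal arms: "N = 39+/-4 (IPFT with alteplase and DNase) and 39+/-4 (pleural irrigation with normal saline"). No section describes stratification, varying block sizes, or central or independent allocation.

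**The concern.** Concealment has two parts. The next assignment must not be readable, and it must not be deducible. A sealed envelope deals only with the first. With a fixed block of 4 and equal allocation, each block holds two of each arm, so earlier assignments in the block constrain later ones. In an open-label trial at one site, earlier assignments can become known to the treating team.

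Someone who knows the next arm could delay, hurry or decline to offer enrolment to a particular patient. There is some room for this. Section 3.6 leaves several decisions to one clinician, including that "when to initiate intrapleural t-PA/DNase is determined by the chest physician", and the chest physician also performs the ultrasound that confirms a complex effusion before randomisation. There could also be a motive, since section 2.4 expects the fibrinolytic arm to do better on drainage, inflammatory markers, hospital stay and surgical referral.

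If the arms differed in prognosis because of such steering, intention-to-treat analysis would not repair it, because the selection happens before randomisation. The Statistical Analysis section plans unadjusted two-group tests, which would not repair it either.

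**Working it through.** **Inputs.** Fixed block of 4 (section 3.6); equal arms, so 2 + 2 per block, and 39 per arm or 78 in total, with a stated range of ±4 per arm giving 70 to 86 (section 3.3); open label and one centre (section 3.1). The documents give no figure for predictability, so there is none to reproduce. The total of 78 is taken as planned; the proportions below hardly depend on it.

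**Assumption about the observer.** They know the block size, see all earlier allocations in order, and so know where each block starts.

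**One block of 4** (six equally likely orders):

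| Position | Probability the arm is known | Probability the best guess is correct |
|---|---|---|
| 1 | 0 | 1/2 |
| 2 | 0 | 2/3 |
| 3 | 1/3 (first two match) | 1/3 × 1 + 2/3 × 1/2 = 2/3 |
| 4 | 1 | 1 |
| Sum | 4/3 | 17/6 |

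In complete blocks, the share known is (4/3)/4 = 1/3 and the share guessed correctly is (17/6)/4 = 17/24 = 70.8%.

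**Over the planned sample.** 78 = 19 complete blocks + 2 patients.

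- Known in advance: 19 × 4/3 + 0 = 25.3, and 25.3/78 = 32.5%.
- Guessed correctly: 19 × 17/6 + 1/2 + 2/3 = 55.0, and 55/78 = 70.5%.
- At 70 patients (17 blocks + 2): 17 × 4/3 = 22.7, or 32.4%. At 86 (21 blocks + 2): 21 × 4/3 = 28.0, or 32.6%.

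These are expectations. The floor is one in four (each block's last place); a third of blocks give two in four.

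**Effect of varying the block size.** Sizes 4 and 6 were drawn with equal probability and simulated over 78 patients, with an observer who knows the possible sizes and updates on every allocation:

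| Scheme | Known with certainty | Best guess correct |
|---|---|---|
| Fixed 4 | 32.5% | 70.5% |
| 4 and 6 | about 5.5% | about 69.1% |

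The guess rate hardly moves because the best guess is simply the arm that is behind so far, which requires no knowledge of the sizes. A check over complete blocks agrees: a block of 4 yields 17/6 correct guesses and a block of 6 yields 6 × 41/60 = 41/10, so (17/6 + 41/10)/10 = 69.3%.

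**What steering could do (illustration on assumed values).** Suppose every known slot were used, so that patients in those slots differed between arms by D standard deviations of the outcome. The spurious difference would be 0.325 × D, against a standard error of √(2/39) = 0.226 standard deviations. At a nominal two-sided 5% level, the false-positive rate would be about 6.5% for D = 0.25, 11% for D = 0.5 and 30% for D = 1. The documents give no basis for choosing D.

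**The case against.** The strongest reply is that predictability on paper is not predictability in practice. The observer must know the block size, see every allocation in order and know where blocks begin. Section 3.2 draws patients from medical and non-medical wards, and section 3.1 gives two years of recruitment, so 78 patients is 78/24, or about 3 a month. A block would take more than a month to fill. The documents do not say who enrols or who sees the running sequence. Entry also rests largely on measurable criteria (section 3.4), which narrows the room to steer, and section 3.6 already places consent, demographic data and baseline imaging before randomisation.

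Most of this stands, and it limits the conclusion. A reader might infer that recruiters do know a third of allocations, or that the comparison is biased; the documents support neither. A reader might also round the count to 26 of 78, but 78 is not a whole number of blocks, and the expected count is 25.3.

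The reply does not remove the opportunity. The size is printed in the protocol, there is one unstratified sequence, and a chest physician team at a single hospital could follow about three allocations a month. Objective criteria still leave discretion over whether and when enrolment is offered. Section 3.6 does not tie opening the envelope to completion of consent and baseline entry.

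It is also fair to object that varying the block size does little to the guess rate. That is correct, and it is why varying the size is not enough alone.

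**Conclusion.** The point holds as an avoidable opportunity for selection bias. Under the stated rule, a recruiter who knows the block size and tracks the sequence could know on average 25.3 of 78 allocations in advance (32.5%) and guess about 70.5% correctly, and sealed envelopes do not prevent it. The enumeration is exact. Its application here is conditional on someone involved in enrolment tracking the sequence, which the documents neither state nor exclude. They support no statement that bias has occurred, and none about its direction or size. The change is worth making because it is cheap and because selection before randomisation cannot be reliably undone in the analysis.

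**What to change.** In section 3.6, replace the fixed block of 4 with permuted blocks of randomly varying size, for example 4 and 6. Have the list prepared by someone not involved in recruitment, and leave the block sizes out of the protocol version that recruiters see. Specify sequentially numbered opaque sealed envelopes, opened only after consent and baseline entry are complete, and say who holds them. Numbering and opacity would be additions, since the protocol now says only that the envelope is sealed.

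Treat these as one package. Varying the size cuts certain knowledge from 32.5% to about 5.5% even for an observer who knows the possible sizes. Keeping the sizes undisclosed is essential because it takes away the basis for what certainty remains. Neither step brings the guess rate much below 69%, so separating list-holding from enrolment matters too, and the residual guessing should be acknowledged.

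The cost is a new list, an independent person to prepare it, a restricted annex for the block sizes, a few sentences of text and minor administration. The final imbalance stays small: at most 3 patients if recruitment stops inside a block of 6, against at most 2 with blocks of 4. If recruitment has started, apply the change to the remaining patients and report the method used before it.

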### Medication Regimen :

t-PA (Alteplase) 5mg and DNase (Pulmozyme)5mg

t-PA (Alteplase) that is available in our pharmacy is 50mg ampoule and DNase (Pulmozyme) is 2.5mg per ampoule

The number of installation of intrapleural t-PA/DNase depends on the discretion of the treating physician (at least 6 hours apart between each dose). 5mg of Alteplase (t-PA) and 5mg DNase are diluted in each 50ml of 0.9% sodium chloride solution. t-PA and DNase are not mixed together in one syringe. The detailed method of t-PA/DNase therapy administration is described in Appendix 1. In brief, both medication are administered sequentially which t-PA is first instilled intrapleurally and the chest tube is then clamped for 45 minutes, then unclamped to allow free drainage for 45 minutes. The same procedure is then repeated for DNase. Selection of the timing of treatment and removal of chest tube are depending on the chest physician's judgement.

However, as for patients who were randomized into pleural irrigation group, subjects were administered 250 ml of 0.9% sodium chloride via chest tube a three way tap from a drip stand which were allowed drainage freely over 1 hour. Pleural irrigation will be performed minimum of 3 installations and maximum of 9 installation (3 times per day).

Both groups received standard care of treatment : which includes regular flushing of chest drain to maintain patency using 20mls of normal saline.

The primary outcome was to evaluate the volume of pleural effusion drainage (in mls) 72 hours following randomization. The volume drained measured after subtracting the amount of volume administered as per protocol.

The secondary outcome are measured by the change in the area of pleural opacity in chest x-ray (day 7 post t-PA/DNase compared to baseline), measured as the percentage of the ipsilateral hemithorax occupied by effusion. The area of pleural opacity and the area of the ipsilateral hemithorax will be measured digitally by two radiologists using Horos Project Software, v3.2.1 as described previously in Multicentre Intrapleural Sepsis Trial 2 (MIST-2)

Other outcomes that will be monitored include :

1. Inflammatory markers including serum C-reactive protein (CRP) & white blood count
2. Length of hospital stay in days
3. The need of surgical intervention within 30 days
4. Adverse effects :
  - a. Chest pain required escalation of analgesics
  - b. Systemic bleeding
  - c. Pleural bleeding

During any point of treatment subjects will be allowed to cross-over and analysis will be done as per intention to treat. Subjects in the pleural irrigation group may be switched to IPFT group if there is poor response to treatment (poor drainage of effusion), or adverse effects of irrigation as per clinician's judgement. On the contrary, subjects in the IPFT group may be switched to pleural irrigation group if patient developed any adverse effects of IPFT (e.g hemothorax, haemoptysis). Those who failed both treatment will be referred for surgical intervention

Monitoring Parameters :

a. Pleural irrigation group

Parameter	Day0	Day1	Day2	Day3	Day7	Day30
Investigations						

 
• Full blood count (FBC)               
 
○ WBC
 
○ Hemoglobin
 
 
 
	√	√	√	√	√	
• C- reactive protein (CRP)	√				√	
• Chest X-ray	√				√	
• Ultrasound Thorax	√	√	√	√		
Adverse effects						
• Chest pain required escalation of analgesics		√	√	√		
• Gastrointestinal bleed		√	√	√		
• Bleeding from chest drain site		√	√	√		
• Intrapleural hemorrhage		√	√	√		
• Hemoptysis		√	√	√		
• Clinical deterioration – hypotension, dyspnea		√	√	√		
• Hb drop >10% required transfusion blood		√	√	√		
• Death related to intrapleural saline irrigation		√	√	√		

Others Outcome						
• Mortality						
• Surgical intervention						

b. IPFT group

Net Volume of pleural fluid drained (ml) post pleural irrigation	Baseline	Day 1	Day 2	Day 3
	√	√	√	√
Cumulative pleural fluid drained post pleural irrigation				√

b. Intrapleural fibrinolytic group

Parameter	Day0	Day1	Day2	Day3	Day7	Day30
Investigations						
• Full blood count (FBC) 
 
○ WBC
 
○ Hemoglobin
 
	√	√	√	√	√	
• C- reactive protein (CRP)	√				√	

• Chest X-ray	√				√	
• Ultrasound Thorax	√	√	√	√		
Adverse effects						
• Chest pain required escalation of analgesics		√	√	√		
• Gastrointestinal bleed		√	√	√		
• Bleeding from chest drain site		√	√	√		
• Intrapleural hemorrhage		√	√	√		
• Hemoptysis		√	√	√		
• Clinical deterioration – hypotension, dyspnea		√	√	√		
• Hb drop >10% required transfusion blood		√	√	√		
• Death related to intrapleural therapy		√	√	√		
Others Outcome						
• Mortality						
• Surgical intervention						

Net Volume of pleural fluid drained (ml) post IPFT	Baseline	Day 1	Day 2	Day 3
	√	√	√	√
Cumulative pleural fluid drained post IPFT				√

[figure not shown]
Operational Definition:

[figure not shown]
- Treatment success: significant amount of pleural drainage post intervention, reduction of opacity on chest x-ray and resolution of inflammatory markers on day 7 without surgical intervention within 30days
- Treatment failure:
  - Poor drainage from chest drain, failure of resolution of pleural effusion or empyema at least 50% reduction on opacity on chest x-ray and clinical evidence of ongoing infection that requires surgical intervention within 30days post randomization or death before discharge.

All patients will be followed up in respiratory clinic day 30 after discharge or phone call if patient defaulted clinic appointment.

Data will be collected prospectively (Appendix 5) by reviewed patient demographics, clinical data on length of hospital stay, pleural fluid analysis, intrapleural therapy, radiographic characteristics, adverse events, Laboratory data (blood leukocyte count, C-reactive protein, haemoglobin level), Intrapleural therapy data including number of chest tubes, duration of chest tube in pleural cavity and cumulative volume of pleural fluid drained. Besides that, length of hospital stay, treatment outcomes, surgical interventions and the occurrence of complications are recorded.

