### 2.2 Primary Objective:

- To measure the volume of pleural effusion drainage (in mls) 48 hours following randomization

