### 2.3 Secondary Objectives:

- To determine the reduction of pleural opacity (in percentage) on chest radiograph from day 1 (randomization) to day 7
- To determine the change on inflammatory markers (WBC/CRP) from day 1 (randomization) to day 7
- To determine the outcome :
  - Length of hospital stay (in days) after randomization for each group
  - The need of surgical intervention in 30 days
  - Adverse effects following t-PA/DNase and pleural irrigation
  - Mortality rate at 30 days

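### The plan does not require the two radiologists who trace chest X-ray opacity in this open-label trial to be masked, and does not say how their two readings are combined

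*Combined protocol and SAP*

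**What the plan says.** Section 3.1 describes a "Prospective open-label study on patients with pleural infection". The first secondary objective in section 2.3 is "To determine the reduction of pleural opacity (in percentage) on chest radiograph from day 1 (randomization) to day 7". Section 3.6, under Medication Regimen, says that the opacity area and the area of the hemithorax on the same side "will be measured digitally by two radiologists using Horos Project Software", with the method given by reference to the MIST-2 trial. That is all the plan says about how the films are read.

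The X-ray also enters the operational definitions that follow the monitoring tables in section 3.6. Treatment success includes "reduction of opacity on chest x-ray and resolution of inflammatory markers on day 7". The definition of treatment failure mentions "at least 50% reduction on opacity on chest x-ray", together with poor drainage and ongoing infection leading to surgery within 30 days, or death before discharge.

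The primary objective is a different measure: "To measure the volume of pleural effusion drainage (in mls) 48 hours following randomization". (Section 3.6 gives 72 hours; that mismatch is a separate matter.)

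**The concern.** Where an effusion ends and consolidated lung or thickened pleura begins is for the reader to decide. A reader who knows the arm, and knows which film is the later one, can be drawn towards the expected answer without intending it. The expected answer is on record: section 2.1 asks whether intrapleural fibrinolytic therapy (IPFT) is superior to irrigation, and four of the five hypotheses in section 2.4 favour IPFT.

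The treating team cannot be masked, and the plan leaves several decisions to it: the number of t-PA/DNase instillations, tube removal and crossover. Film reading is a judgement that can be shielded from knowledge of the arm. A team that followed the plan to the letter could read every film with arm and date in view. A difference in opacity between arms would then be hard to defend, even if it were real.

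**Working it through.** **1. What the plan says about the readers.**

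| Question | What the plan states |
|---|---|
| Who reads? | Two radiologists, digitally (3.6) |
| Masked to arm, identity, date or film order? | Not stated |
| Independent of the treating team, or of each other? | Not stated |
| How do two readings become one value? | Not stated |
| Method? | By reference to MIST-2; content not reproduced |

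The statistical analysis section (the second section numbered 3.7) does not fill these gaps.

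**2. Can masking be done?** Section 3.6 gives all patients a chest drain, and both monitoring tables schedule films at Day 0 and Day 7. Neither the film schedule nor the presence of a drain therefore identifies the arm. Film date is harder to hide. The baseline film is taken with the tube in place, removal is at the physician's discretion, and a day-7 film without a tube reveals its timing. This matters less than masking to arm. A reader who knows the date but not the arm has no reason to treat the arms differently, so the expected effect falls on within-group change rather than on the comparison between arms.

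**3. Size for one patient (assumed figures).** The plan gives no figure for reader error, so there is none to reproduce. Let B be baseline opacity and D day-7 opacity, both as a percentage of the hemithorax. The relative reduction is R = (B − D)/B, so with B fixed a tracing difference d at day 7 changes R by d/B.

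- B = 40, d = 3: 3/40 = 7.5 percentage points. For example, D = 21.5 gives 18.5/40 = 46.25%, and D = 18.5 gives 21.5/40 = 53.75%.
- Range for d = 3: B = 30 gives 3/30 = 10 points; B = 60 gives 3/60 = 5 points.

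This is the effect of any tracing difference on one patient. It does not measure bias between arms, which arises only if the differences lean one way by arm.

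**4. Size for the comparison (assumed figures).** Let b be a mean difference between arms, in points of percentage reduction, due to reading alone. Inputs: 39 per arm (section 3.3) and a two-sided 0.05 test. The SD is borrowed from the irrigation trial's CT volume change, whose interquartile ranges are in section 3.3, as a stand-in for X-ray opacity:

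- (43.7 − 19.6)/1.349 = 17.9
- (28 + 5.5)/1.349 = 24.8

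The standard error is SD × √(2/39), which is 4.05 to 5.62. The false-positive rate is Φ(b/SE − 1.96) + Φ(−b/SE − 1.96):

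| b (points) | SD 17.9 | SD 24.8 |
|---|---|---|
| 0 | 5% | 5% |
| 2 | 7.8% | 6.5% |
| 5 | 23.5% | 14.4% |
| 10 | 69.6% | 42.8% |

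The documents give no value for b, so the table shows only how sensitive the comparison would be.

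**5. Does the 50% line carry the bias into treatment failure?** Not directly. The failure definition is compound: alongside the X-ray it names ongoing infection that requires surgery within 30 days, or death before discharge. Success asks for a reduction in opacity with no threshold. Nothing says that the radiologists' measurement, rather than the clinical team's view of the film, supplies the 50% judgement.

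**The case against.** The strongest reply is that silence is not evidence. A reader might infer that the radiologists are unmasked, but no section says so. Open label describes treatment, not film reading, and decisions about therapy rest with the chest physician. The method is used "as described previously in Multicentre Intrapleural Sepsis Trial 2 (MIST-2"), and that source, which cannot be checked from these documents, may include masked reading. This stands, and it limits the point to what the plan requires. It does not remove the point, because a cross-reference attached to an area measurement does not expressly adopt masking.

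Three stronger readings also go too far:

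- Opacity is not the only efficacy measure protected from the treating team's judgement. CRP and white cell count are laboratory values, and 30-day mortality needs no reader.
- Reader bias cannot simply move patients between success and failure at the 50% line, because the failure definition is compound.
- Opacity is not central to the trial's claim. It is secondary, and none of the hypotheses in section 2.4 names it, although the research question favours IPFT generally.

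It is also fair to say that tracing error of equal size and direction in both arms would not favour IPFT. Only error that differs by arm does, and masking to arm is the protection against that.

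**Conclusion.** The point holds as a gap in the plan. In an open-label trial with a stated expectation in favour of IPFT, a judgement-based secondary outcome has no stated masking of its readers and no rule for combining their readings. It is a cheap improvement to a secondary outcome. It does not touch the primary outcome, and it changes neither sample size nor power.

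The size of any bias is unknown. The 7.5-point shift for one patient rests on an assumed 40% baseline and an assumed 3-point difference. The false-positive rates rest on an assumed bias and a borrowed SD. Neither shows that bias will occur. If masked reading is already the practice, stating it, together with the rule for combining the readings, settles the point.

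**What to change.** Where section 3.6 describes the X-ray measurement, state that:

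- baseline and day-7 films are exported with patient ID, date and arm removed;
- they are presented in random order to the same two radiologists;
- each radiologist reads independently, and both readings are recorded;
- the mean of the two readings is analysed.

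Reporting agreement between the readers would be a useful addition, since both readings will be on file.

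The cost is a few minutes of anonymisation per film, with no extra films, visits or readers. It is small rather than nil, and the budget in section 3.8 lists only drugs. The limit is that a day-7 film without a chest tube may give away its date; the plan should acknowledge this. The change can be applied to stored films after enrolment has begun, provided that the masked readings are made before the outcome is analysed.

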## **OBSERVATION AFTER ADMINISTRATION OF t-PA (ALTEPLASE) & DNase (PULMOZYME)**

1. Observe the patient for:
  - a. deterioration in clinical condition
  - b. tension pneumothorax
  - c. hemorrhage from site or excessive drainage (in excess of 1L per hour) in drainage bottle
2. Monitor for:
  - a. Bedside ultrasound of thorax (by chest physician) daily with curvelinear probe (ultrasound Mindray, model Z5) by measuring the maximum distances between the parietal and visceral pleural.
  - b. Serial chest x-ray (baseline x-ray, day 7 post t-PA/DNase and pleural irrigation)
  - c. Serum CRP level (baseline, day 7 post t-PA/DNase and pleural irrigation)
  - d. FBC (baseline, day 1- 3, day 7 post t-PA/DNase and pleural irrigation). Drop of

hemoglobin by less than 10% from baseline is acceptable.

- e. Systemic bleeding/ Pleural bleeding
  - f. Drainage of pleural effusion daily
3. Stop the t-PA & DNase if there is significant drop of haemoglobin (>10% drop Hb) with clinical signs of shock or significant haemorrhagic fluids drained. Consider CTA and blood transfusion in those cases

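### The only haemoglobin adverse-effect row requires a transfusion, unlike the 10% criterion in Appendix 1, and systemic bleeding outside the gut and airway has no dedicated row

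*Combined protocol and SAP*

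**What the plan says.** Section 2.3 makes adverse effects of both treatments a secondary objective. The texts that bear on haemoglobin and bleeding are these:

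- **Section 3.6, Monitoring Parameters, both arms, and the Data Collection Sheet, Outcome Monitoring.** The haemoglobin row is "Hb drop >10% required transfusion blood". The other bleeding-related rows are gastrointestinal bleed, drain-site bleeding, intrapleural haemorrhage, haemoptysis, and clinical deterioration with hypotension or dyspnoea. In section 3.6 these rows are ticked for Days 1 to 3.
- **Appendix 1, Observation, item 2d.** A drop of "hemoglobin by less than 10% from baseline is acceptable". Transfusion is not mentioned.
- **Appendix 1, Observation, item 3.** The text on stopping t-PA/DNase refers to "significant drop of haemoglobin (>10% drop Hb) with clinical signs of shock or significant haemorrhagic fluids drained". Transfusion is something to consider afterwards ("Consider CTA and blood transfusion in those cases") and not part of the criterion.
- **Section 3.6, list of other outcomes.** "Systemic bleeding" is one of the three adverse effects named. It is not defined there, nor in Appendix 1 item 2e, which asks for it to be monitored.

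The full blood count, including haemoglobin, is scheduled on Days 0, 1, 2, 3 and 7 in both arms. Section 3.6 lists haemoglobin among the laboratory data to be collected, and says that complications are recorded.

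**The concern.** Bleeding is an obvious safety question when a fibrinolytic is compared with saline. The haemoglobin row adds a treatment decision to a laboratory criterion. The study is open-label (section 3.1) and gives no transfusion threshold, so whether the row is ticked reflects how readily clinicians transfuse, and where the patient's haemoglobin started, as well as how far it fell. Two patients can then be classified in the reverse order of their falls.

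For systemic bleeding, the outcome list is broader than the rows that are meant to capture it. A urinary or intracranial bleed, for example, has no row of its own. Such events are foreseeable: Appendix 1 has guidance for participants on warfarin, rivaroxaban, apixaban or dabigatran.

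At stake is whether the safety comparison set as an objective rests on events that are defined in advance and recorded alike in both arms.

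**Working it through.** The point is about an outcome definition, so the plan has no figure to reproduce. The check sets the texts side by side and then asks how much can be said about size.

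**1. Three haemoglobin criteria**

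| Place | Fall | Further condition |
|---|---|---|
| Section 3.6 rows and Data Collection Sheet | >10% | transfusion |
| Appendix 1, item 2d | <10% acceptable | none |
| Appendix 1, item 3 | >10%, called significant | shock or haemorrhagic drainage |

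The three do not coincide. A fall above 10% without transfusion meets no haemoglobin row. If there is also no drain-site, pleural, gastrointestinal or airway bleeding and no hypotension or dyspnoea, it meets no listed adverse-effect row at all.

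**2. What the transfusion condition does** (illustrative values; the documents give none)

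Percentage fall = 100 × (baseline − lowest) / baseline.

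- 11 to 8.5 g/dL, not transfused: 100 × 2.5/11 = 22.7%. Haemoglobin row not met.
- 8 to 7.1 g/dL, transfused: 100 × 0.9/8 = 11.3%. Haemoglobin row met.

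Suppose transfusion follows once haemoglobin reaches a level L of 7, 8 or 9 g/dL. This is an assumption made only to show the dependence on baseline. The fall needed is 100 × (1 − L/baseline):

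| Baseline (g/dL) | Value after a 10% fall | L = 7 | L = 8 | L = 9 |
|---|---|---|---|---|
| 8 | 7.2 | 12.5% | already there | already there |
| 9 | 8.1 | 22.2% | 11.1% | already there |
| 11 | 9.9 | 36.4% | 27.3% | 18.2% |
| 12 | 10.8 | 41.7% | 33.3% | 25.0% |
| 13 | 11.7 | 46.2% | 38.5% | 30.8% |

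The same nominal 10% criterion therefore corresponds to very different falls, depending on baseline and practice.

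**3. How many falls could be missed**

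Let t be the share of >10% falls that are transfused, and o the share of the untransfused falls caught by another row. The share in no adverse-effect row is (1 − t)(1 − o). Both inputs are assumptions.

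| t | o = 0 | o = 0.50 | o = 0.75 |
|---|---|---|---|
| 0.10 | 90% | 45% | 23% |
| 0.25 | 75% | 38% | 19% |
| 0.50 | 50% | 25% | 13% |
| 0.75 | 25% | 13% | 6% |

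For example, 0.90 × 0.50 = 0.45 and 0.25 × 0.25 = 0.0625. The range is too wide to support any statement about a majority.

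**4. Systemic bleeding against the rows**

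Drain-site bleeding and intrapleural haemorrhage are local. That leaves "Gastrointestinal bleed" and haemoptysis as the only site rows that can stand for systemic bleeding. This mapping is a reading, since the documents give none. There is no row for another site.

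**5. Timing**

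Haemoglobin is measured on Day 7, but the adverse-effect rows in section 3.6 are ticked only for Days 1 to 3. A fall first seen on Day 7 is outside the ticked window.

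**The case against.** The strongest reply is that the data are not lost. Haemoglobin is recorded on five days in both arms, so any fall above 10% can be derived for every patient. Drain-site, pleural, gastrointestinal and airway bleeding and hypotension have rows that need neither a transfusion nor a haemoglobin change. The transfusion row can be read as a severity marker beside them. A bleed elsewhere might still appear under clinical deterioration, under the transfusion row, or in the general recording of complications.

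Much of this stands, and it limits the point. A reader might infer that most significant falls will go uncounted. The documents do not support that: they give no rate of falls or transfusions, and the values themselves are collected. A reader might also infer that the safety comparison leans toward no difference. That does not follow either. Randomisation balances baseline haemoglobin in expectation, a stricter definition lowers counts in both arms, and clinicians alert to t-PA bleeding might transfuse that arm more readily.

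What the reply does not supply is a pre-specified outcome. Haemoglobin change is not among the outcomes in sections 2.3 or 3.6, and the Statistical Analysis section names no such analysis. A cut-off chosen after open-label data have been seen would be weaker. Recording complications without itemising them does not define systemic bleeding.

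**Conclusion.** The point holds as a gap in outcome definition. As written, an untransfused haemoglobin fall above 10% with no other listed sign is not tabulated as an adverse effect, although Appendix 1 calls a fall of that size significant. Whether the haemoglobin row is met depends partly on an unmasked transfusion decision with no stated threshold. Bleeding at a site other than the drain, pleura, gut or airway has no dedicated row, although systemic bleeding is a named outcome.

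The documents do not fix the size. The 6% to 90% range rests wholly on assumed shares, and the direction of any bias is unknown. It would also go too far to say that the protocol calls these falls unacceptable. Appendix 1 says that less than 10% is acceptable and labels more than 10% significant; unacceptability is only implied, and its stopping text adds shock or haemorrhagic drainage. This is a cheap improvement to a secondary safety outcome and does not bear on the primary comparison.

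**What to change.** - Pre-specify a haemoglobin-fall outcome of more than 10% from Day 0, the protocol's own threshold. Compute it in both arms from the scheduled blood counts on Days 1, 2, 3 and 7, regardless of transfusion.
- Record transfusion as a separate yes/no row.
- Add a row for systemic bleeding at another site, with the site to be specified, to both schedules in section 3.6 and to the Data Collection Sheet.
- Reconcile the haemoglobin wording in section 3.6, the Data Collection Sheet and Appendix 1. No stopping or transfusion rule is proposed here.

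The cost is a few wording changes in two schedules and one data sheet, with no new blood test. The downside is that more haemoglobin events will be reported, some unrelated to bleeding, which could dilute the comparison. They should therefore be shown beside the overt-bleeding and transfusion rows and not in place of them.
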